Salivary Cortisol and mSSS ^{8*}			X			
Dependent Variables (Aim 2)						
Physiological Response (Blood Pressure, Pulse)					X	X
Subjective Response (SSS) ⁹					X	X
Behavioral Response (FT, WR, 2B, IMT, DMT) ¹⁰					X	X
Plasma Nicotine						X
Other Items						
Informed Consent	X					
Liver Function Tests ¹¹	X					
Demographics	X					
Medical History	X					
Smoking Behavior ¹²	X					
Adverse Events (including C-SSRS)	X	X		X	X	X
Expired Carbon Monoxide	X	X		X	X	X
Urinary Cotinine and 3-Hydroxycotinine		X		X		X

These items will be collected five times during the course of Day 5 only – at waking, 30 minutes later, two hours later, 8:00 pm and at bed time. ¹ Minnesota Nicotine Withdrawal Scale, Hughes & [name], 1998; ² Brief Questionnaire of Smoking Urgency, Tiffany & Drobes, 1991; ³ Modified Cigarette Evaluation Questionnaire, Cappelleri et al, 2007; ⁴ Positive and Negative Affect Schedule, Watson et al, 1988; ⁵ Cohen Perceived Stress Scale, Chaaya et al, 2010; ⁶ Center for Epidemiologic Study – Depression Inventory, Derogatis & Spencer, 1982; ⁷ Modified Subjective State Scale, [name], et al., 1998, [name] et al, 2003; ⁸ Lesiure Time Exposure Questionnaire, Godin & Shephard, 1983; ⁹ Subjective State Scale, [name], et al., 1998 and [name] et al, 2003; ¹⁰ Behavior tasks include Fingertapping, Hindmarch, 1980, Word Recall, Phillips & Fox, 1998, 2-Back, Meyers et al, 2008, Immediate Memory Task, Dougherty et al, 2002; ¹¹ Liver function tests of ALT and AST will be conducted in Sample 2 (OC only). ¹² Includes Fagerstrom Test of Nicotine Dependence (FTND), age of smoking initiation, number of past quit attempts, longest past quit attempt, motivation to quit smoking and TimeLine FollowBack (TLFB).

support for cessation. Based on observations in our current study, it is expected that up to 20% of women will want to maintain their smoking abstinence. If the participants want to return to smoking, they will be instructed to smoke at their 'regular rate' for the next three weeks and then attend an identical second testing period during the opposite testing phase (i.e. "low" or "high" dose).

Data Collection Procedures. All participants (Sample 1 and Sample 2) will complete identical testing procedures as described below and in **Table 2**.

The first visit will be a *screening visit*. At this visit informed consent will be obtained, followed by collection of demographic and smoking behavior information. Medical histories will be collected to further evaluate eligibility. The Columbia-Suicide Severity Rating Scale (C-SSRS) will be completed with each subject in order to assess suicidal ideation or behavior. Results will be reviewed by study staff and participants will be referred to physicians ([name], MD) or ([name], PhD) if necessary. Measurements of height, weight (measurements taken with coats, shoes and other heavy items removed), blood pressure (measured after five minutes of rest), heart rate, and carbon monoxide will also be collected. A blood sample will be collected for liver function tests (AST and ALT) for Sample 2 participants only. At the end of this visit the all remaining clinic visits will be scheduled and participants will be compensated for their time.

The *baseline visit (Day 0)* will be the first day of the testing period. At this visit participants will have their weight measured and then be shown into a private room to complete self-reported items of smoking-related symptomatology and related factors (See Table 2 and Section E.5 for details). After the questionnaires are completed, blood pressure, and heart rate will be measured. Next, the participant will provide urine (for assessment of nicotine exposure) and blood (for assessment of sex hormones) samples. Remaining blood and urine samples will be saved in the biorepository. The participants will then be trained on how to use the study supplied Electronic Data Capture Device (EDCD). Upon the completion of this visit, the upcoming visit dates/times will be confirmed and participants will be compensated for their time.

During the *testing period (Days 0-7)* all participants will complete daily *Ecological Momentary Assessments (EMA)* using a study supplied Electronic Data Capture Device (EDCD). The EDCD will be programmed to "beep" to indicate an assessment is available. Given that recent research indicates that smoking-related symptomatology varies by time of day³⁶ participants will be prompted to complete assessments at random times (between the hours of 7AM and 11PM) up to four times per day, for an average of three times per day. Notification of an available assessment will happen via a "beep" sound. The EDCD will continue to "beep" once per every 15 minutes until the assessment is completed or after the two-hour window allotted for completion of assessment elapses. Each assessment will take an estimated 15 minutes to complete and will measure self-reported levels of smoking, withdrawal, craving, mood, stress, and physical activity (See Table 2 and Section E.5. for details). We have opted to use EMA due to several benefits versus standard paper-and-pencil format including improved quality of data, increased participant compliance, and participant preference.³⁷⁻³⁸

[figure not shown]
The interim clinic visit (Day 3 or Day 4), participants will return to the clinic. Upon arrival, participants will have their weight measured, followed by measurement of blood pressure, heart rate and carbon monoxide. Cigarettes smoked per day since Day 0 will be collected retrospectively from participants. Participants will also be asked about any new medications or changes to current medications. Participants will receive training on how to do the saliva samples on day 5 and receive the specific materials to do the saliva samples. Any difficulties the participant has had using the EDCD will be addressed before the participant leaves. At the end of this visit the participants will be compensated for their time.

On the day prior to the follow-up visit (*Day 5*) participants will collect salivary cortisol samples outside the clinic to measure physiological stress levels. Participants will be reminded to collect saliva samples via prompts from the EDCD. We are measuring saliva cortisol rather than blood serum levels, because samples are needed throughout the day and multiple blood draws are impractical, burdensome and would impose ethical issues in pregnancy. Saliva sample collection will occur at the following times to assess the diurnal pattern of cortisol: immediately after waking, 30 minutes later, two hours later, 8:00 pm and before going to sleep. We have successfully used this method in prior projects,^{14, 39} as well as in our ongoing study. Participants are compliant with the testing procedures. Participants will be supplied with saliva sample swabs (Salivette™ tubes, Sarstedt, Rommelsdorf, Germany). Tubes will be labeled to indicate the date and time each sample should be completed. Previous research has shown that this ambulatory monitoring procedure can be adequately performed by participants, and that the integrity of the salivary cortisol is not compromised by storage at room temperature for 24 hours.⁴⁰ During each saliva sample collection, participants will complete the monitoring Subjective State Scale (mSSS) via the EDCD to monitor mood and potential confounders such

as time of last cigarette, physical activity, and caffeine use (Appendix B).

At the *follow-up clinic visit (Day 6)*, participants will return to the clinic. Upon arrival, participants will have their weight measured and provide urine (nicotine exposure and medication compliance via visual inspection of urine color which will change due to riboflavin medication filler) and blood (sex hormones) samples. Remaining blood and urine will be saved in the biorepository. Next, participants will complete self-reported items of smoking-related symptomatology and related factors (See Table 2 and Section E.5 for details) followed by measurement of blood pressure and heart rate. While participants are completing the questionnaires study staff may complete a NicAlert (Appendix C) to confirm self-reported smoking status (NicAlert level of ≥ 3 indicating a cotinine value of ≥ 100 ng/mL). Participants will then practice using the nicotine nasal spray but will be prompted to refrain from smoking for one hour prior to the visit to limit nicotine exposure. They will also practice smoking through the smoking topography machine and practice using the computer tasks and other measures used in the lab sessions (See Section E.5. for details). Finally, participants will be instructed to quit smoking by midnight (Appendix D). Upon the completion of this visit, the lab session will be confirmed and participants will be compensated for their time.

Figure 6. Nicotine Lab Sessions

The *smoking lab session*

will occur on *Day 7*. At this visit, participants will smoke their first morning cigarette (i.e. they will be instructed to not smoke on Day 7 until instructed to do so by study staff). Participants will attend a three hour visit beginning as close to their usual first morning cigarette as possible (starting at approximately 7am-10am, per participant preference). Puff topography, a precise measure of smoking behavior,^{67,68,69} will be used to examine whether prolonged use of progesterone affects topography measures that may indicate smoking compensation.⁷⁰ Puff topography will be assessed using a handheld topography device (type pending) that provides a valid measurement of puff number, puff volume, inter-puff interval and other indices.⁶⁶ Carbon monoxide readings will be collected before and 2-5minutes after puff topography.³⁶ Prior to the initiation of the lab session, participants will have their weight, blood pressure, and heart rate measured, and they will complete subjective measures to assess their self-reported level of smoking-related symptomatology and related factors after overnight abstinence (See Table 2 and Section E.3.5 for details). Once the smoking lab session begins, participants will be instructed to turn off their cell phones and will not be allowed to consume caffeinated beverages or any food items. Measurements of smoking response will start 40 minutes prior to the participant smokes her cigarette and will be administered in a fixed order (**Figure 6**). Response to smoking will be quantified via seven performance domains known to be associated with nicotine response:⁴¹ (1) physiological (blood pressure, heart rate), (2) subjective (Subjective State Scale); (3) motor speed (Finger Tapping) (4) episodic memory (Word Recall); (5) working memory (2-Back); (6) attention/impulsivity (Immediate Memory Task), and (7) delayed memory (Delayed Memory Task). (See Section E.5. for more details.) In order to access plasma nicotine levels, a blood draw via an intravenous catheter will occur at baseline (-1 minute before smoking a cigarette) and +2 minutes after the last puff of the cigarette. A total of 30cc of blood will be collected. 15 cc of blood will be analyzed for nicotine levels and hormone levels and 15 cc of blood will be added to the biorepository.

The *nicotine exposure lab session* will occur on *Day 8*. Participants will attend this four and a half-hour visit in the morning (beginning at 7am-10am depending on participant preference) to control for diurnal variation in outcome variables. While participants are completing the questionnaires study staff will download the information from the EDCs. Procedures will be identical to Day 7 except instead of subject smoking a cigarette, they will administer nicotine nasal spray and repeat the protocol twice. Nicotine nasal spray (Nicotrol, Pharmacia & Upjohn; Appendix A) is an FDA-approved use of nicotine delivery. One spray delivers 0.5 mg of nicotine; therefore, one dose (four sprays - two in each nostril) is approximately equivalent to the

nicotine delivery from two cigarettes.⁴²⁻⁴⁴ The nasal spray is the only available delivery method that closely mimics the kinetics of smoking, is easy to administer, and delivers a consistent dose.⁴²⁻⁴³ While the nicotine nasal spray results in an adverse burning sensation, this sensation resolves on its own within minutes. In our current study we have completed over 400 nicotine nasal spray lab sessions and have never had to postpone data collection due to problem with the adverse effects of the nasal spray. We also chose the nicotine nasal spray because: (a) there are ethical and practical difficulties of instructing people to inhale measurable amounts of tobacco smoke from cigarettes, (b) it is difficult to control nicotine intake via smoke inhalation, (c) the spray isolates the effects of nicotine from that of the many other compounds found in tobacco smoke, (d) it has the fastest delivery system and best approximates the rise in nicotine concentrations as seen with cigarette smoking, and (e) it has been given a Pregnancy Category Risk of D – indicating that although nicotine has known adverse effects, the benefits of use may outweigh the risks. While there may be some initial concerns with administering nicotine to a pregnant woman, nicotine replacement products have been recommended for smoking cessation during pregnancy.⁴⁵ In a recent study by Oncken and colleagues,⁴⁶ 11 doses of nicotine nasal spray were administered over a six-hour period in a sample of pregnant smokers who abstained from smoking overnight. This study found that nicotine nasal spray reduced overall maternal nicotine exposure compared to active smoking. Compared to the 11 doses used in this study, our study will be using a single dose of nicotine nasal spray (less than 5% of the acceptable maximal dose and less than 10% of the dose used by Oncken and colleagues); therefore, there are limited ethical concerns with using nicotine nasal spray within our sample of pregnant smokers. Further this protocol was reviewed by a bioethicist at the University of Minnesota, [name], who felt there were no major ethical issues in administering this dose of nasal nicotine spray to pregnant women (see Section 2.14 for letter of support). In order to access plasma nicotine levels, a blood draw via an intravenous catheter will occur at baseline (-1 minute before the nasal spray) and at the expected maximum concentration (+5 minutes after the nasal spray; [name] et al, 2012). Blood collected at baseline will also be used to analyze sex hormones, more specifically progesterone and allopregnanalone. A total of 30cc of blood will be collected, 15 cc of blood will be analyzed for nicotine levels and hormone levels and 15 cc of blood will be added to the biorepository. Participants will also provide a urine sample to assess nicotine exposure and medication compliance via visual inspection of urine color which will change due to riboflavin medication filler. Remaining urine will be saved in the biorepository. Upon completion of the four and a half-hour lab session, any possible adverse events will be assessed for all participants. Finally, all participants will be compensated for their time and will be offered brief smoking cessation counseling and self help materials for smoking cessation.

Study Participant Compensation. All participants will receive \$10 at the screening visit, \$20 at the baseline visit, \$10 at the interim visit, \$20 for Follow-up Visit on Day 6, \$20 for Smoking Lab Session on Day 7 and \$50 for the Nicotine Exposure Lab Session on Day 8. They will also receive \$5 for each EMA completed with a bonus of \$20 for not missing any EMAs, and \$1 for each cortisol salivary sample collected with a bonus of \$20 for not missing any of the five samples. A bonus of \$100 will be given for completing all study procedures and \$120 for returning the study supplied EDCD. Thus, all participants in Sample 1 will be compensated a total of \$510 for completing the study. The participants in Sample 2 will have the potential to earn \$ 900 by completing the testing week twice.

Study Measures. The independent measures will be the serum levels of progesterone (Prog), allopregnanolone (Allo), and the estradiol/progesterone (E2/P) ratio. Measurement of hormones will be done by collecting a blood sample on the baseline, follow-up, and nicotine nasal spray lab visits (Day 0, 6, and 8). We have opted to collect blood samples three times to allow for average hormone levels during the testing period to be obtained. Blood (20 cc) will be drawn then centrifuged. The serum stored at -20°C in sealed storage tubes to prevent evaporation. Approximately two mL of serum will be analyzed by the Fairview University Medical Laboratories for progesterone and estradiol samples using chemiluminescence. The expected values for these tests are displayed in Figure 6. Approximately two mL of serum will be sent to [name] lab at the University of California, San Diego (see Section 2.14 for letter of support) for Allo level measurement using radioimmunoassay techniques previously described.⁴⁷ The remaining serum (approximately two to four mL) will be stored as back-up.

For Aim 1, the outcome is the level of smoking-related symptomatology during ad libitum smoking. Items 1-7 below will be measured an average of three times a day for seven days via the EMAs. We selected the seven day testing period given that the hormones fluctuate fairly rapidly; thus, measuring symptomatology for longer than seven days would make the association between sex hormones and symptomatology more difficult to assess. For each item, participants will be instructed to rate their symptoms since the last assessment. The following nine dependent measures will be used (Appendix B):

- (1) Minnesota Nicotine Withdrawal Scale (MNWS): Participants rate their nicotine withdrawal symptoms on eight-items on a scale of '0' (not present) to '4' (severe) resulting in summary scores overall withdrawal and craving.²⁵
- (2) Questionnaire on Smoking Urges-Brief (QSU-Brief): This ten-item version of the original form (QSU) was developed by Tiffany and Drobes²⁶ and has an excellent level of reliability ($\alpha = .97$). Two factors are obtained: 'Factor 1' is a measure of primary intention and desire to smoke and 'Factor 2' is a desire to smoke in anticipation of relief from negative affect.
- (3) Modified Cigarette Evaluation Questionnaire (mCEQ): This 12-item questionnaire uses a seven-point Likert-type scale to assess the reinforcing effects of smoking resulting in five domains including smoking satisfaction, psychological reward, aversion, enjoyment of respiratory tract sensations and craving reduction.²⁷
- (4) Positive and Negative Affect Scale (PANAS): Participants rate 20 words associated with positive or negative affect using a five-point Likert-type scale. This scale has been shown to have high internal consistency.⁴⁸
- (5) Cohen Perceived Stress Scale (PSS): This ten-item questionnaire has been validated in a variety of populations including pregnant and postpartum women. It uses five-items to assess ten questions resulting in two factors negative feelings and inability to handle stress. It has high internal reliability ($\alpha = 0.75$).⁴⁹
- (6) Center for Epidemiologic Studies – Depression (CES-D): This form contains ten-items to assess symptoms typically associated with depression. The items are ranked using a four-point Likert-type scale. It has high levels of sensitivity and specificity.⁵⁰⁻⁵¹ We have opted to use this item rather pregnancy-specific item to ensure that all participants had comparable data.
- (7) Leisure Time Exercise Questionnaire (LTEQ): This questionnaire has four-items to assess strenuous, moderate and mild exercise completed during leisure time and has high reliability ($r=0.83, 0.85$).⁵²
- (8) Monitoring Subjective State Scale (mSSS, Day 5 only): This form is identical to the Subjective State Scale (SSS)⁵³⁻⁵⁴ except it also includes variables to assess possible confounders such as coffee consumption. Participants will be asked to mark each rating scale at the point that best describes how they felt over the past 30 minutes.
- (9) Salivary Cortisol (Day 5 only): Five saliva samples over the course of the day given that cortisol, a physiological measure of stress released by the hypothalamic-pituitary adrenal axis (HPAA), has a clear diurnal variation. Its peak activity occurs about 8:00 am in the normal sleeper, followed by steady decline until noon. The lowest activity occurs around 8:00 pm. The frequent sampling in the morning will be used to assess free cortisol responses to awakening. Awakening cortisol increase is considered a promising marker of adrenocortical functional status.⁵⁵⁻⁵⁷

For Aim 2, the outcomes will be assessed following overnight abstinence: (1) the change in smoking-related symptomatology (items 1-6 above), and (2) response to nicotine (described below). We have a nearly identical timed series to assess nicotine response with success in our ongoing study. All items will be self-administered per direction of study staff via a computer program (REDCap; <http://project-redcap.org/>) to improve the quality of data (by avoid missing data, illegible data, etc) and limit amount of time spent on data entry and cleaning. The following seven *dependent measures* were selected to assess seven domains of nicotine response:⁴¹

- (1) Physiological Measures: Blood pressure (BP) and heart rate (HR) will be measured using a Dinamap S X/P. This device is an automated device that will read BP and HR simultaneously by placing a blood pressures cuff above the antecubital fossa region of the arm.
- (2) Subjective Response: The Subjective State Scale (SSS) questionnaire is comprised of 24-items to assess positive affect, distress and nicotine withdrawal symptoms.⁵³⁻⁵⁴ Participants will rank each item based on how they felt over the past 5-30 minutes (depending on time of last completion) using a seven-point scale ranging from 'not at all' to 'very strong.' This form takes approximately two minutes.
- (3) Motor Speed: During the Finger Tapping (FT) task,⁵⁸ participants are instructed to use the index finger on the dominant hand to tap a key on a computer as quickly as possible for 30 seconds. This task takes about 1.5 minutes.
- (4) Episodic Memory: The Word Recall (WR) task presents 25 concrete nouns individually on a computer screen for three seconds each. Upon completion of the display participants will be given a short distractor of counting out loud from "20" to "0." They then complete a written recall of the words within two minutes. The total number of words correct is each participant's score.⁵⁹ This task is designed to assess short-term episodic memory and is estimated to take four minutes.

- (5) Working Memory: The 2-Back (2B) task presents stimuli (letters on a computer screen) for two seconds with a half-second between stimuli. Participants are instructed to press a key when a letter was repeated with one intervening letter (i.e. matched a letter two back in the series). The percent correct responding and mean response times are recorded.⁶⁰ This task takes approximately six minutes.
- (6) Attention/Impulsivity: The Immediate Memory Task (IMT) is a continuous performance task that displays a series of randomly generated 5-digit numbers (e.g., 54983) on a computer monitor for ½ a second at a rate of one per second. The participant is instructed to click a button when the number displayed is identical to the preceding number. Responses to the target stimuli (i.e. correct identification of duplicate numbers) and filler stimuli (i.e. all other random 5-digit) are indicators of response inhibition and continuous attention. The higher the 'catch stimuli' (i.e. a number that differs from the preceding number by only one digit) indicates a more impulsive pattern.²⁴ It is estimated that this task will take approximately six minutes.
- (7) Delayed Memory: The Delayed Memory Task (DMT) is a continuous performance task functions nearly identical to the IMT except a series of distracter sequences (i.e. 12345) are presented between target stimuli. Participants are instructed to ignore these distracters and click the right mouse button in response to target stimuli. Therefore, this task measures delayed memory.²⁴ It is estimated that this task will take approximately six minutes
- (8) Plasma Nicotine (Day 8 only): We will also collect two blood samples (30 cc) through an intravenous catheter one minute prior to nicotine nasal spray and five minutes after. The intravenous catheter will be placed by trained study staff approximately 45 minutes prior to the use of nicotine nasal spray to avoid influencing data collected during the baseline (Time -40 or -1 minutes) assessment. These samples will be frozen and stored to be analyzed for plasma nicotine and sex hormones. These time points were selected to allow for maximum concentrations of nicotine to be captured based on data from our prior work ([name] et al, 2012).

Information on *potential covariates* is collected at the baseline visit. These items include number of cigarettes smoked per day during ad libitum smoking, Fagerstrom Test for Nicotine Dependence (FTND),⁶¹ self-reported number of past quit attempts, past longest quit attempt, motivation to quit smoking, social influences such as partner smoking and sociodemographic variables (Appendix B). Participants in both samples will also complete an adverse events form along with the *Columbia-Suicide Severity Rating Scale* at Screening, Day 0, and Day 8 to assess possible adverse events associated with the study medications. The C-SSRS (Posner et al, 2009) assesses suicidal ideation, given this is listed as an SAE on the Prometrium label. If any item of suicidality is endorsed referrals to the appropriate mental health care will be made.

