To compare the two study samples we will use all data from Sample 1 and data from the first testing period only for Sample 2. To compare outcomes between Sample 1 and Sample 2, we will use a propensity score ⁶⁵ to balance the baseline covariates in the two groups. A linear regression model will be used to investigate the association between Prog and the self-reported craving outcome. An indicator variable for group, the propensity score quintile, Prog and a group by Prog level interaction will be included in the model as independent variables. Similar analyses will be conducted for the secondary outcomes and the independent variables (Allo, E2/P)

Strengths & Limitations. This study has several strengths. First, and foremost, is the use of two unique clinical models to investigate the effects of sex hormones on smoking-related symptomatology. This study will be among the first to utilize this type of study design. Further, the cross-over study design used with Sample 2 will limit confounding given that each participant is compared to herself. An additional strength is the detailed measurement of smoking status, sex hormones, smoking-related symptomatology, withdrawal symptoms and nicotine response. Finally, the study team has extensive experience and expertise, which provides unique qualifications to pursue this research project. Three limitations are worth noting. First, we do not have a sample of males for comparison. The relevance for needing this comparison group may be of lesser importance considering that female sex hormones are the main interest. Second, due to the experimental design and the use of a convenience sample, we will have limited generalizability. Finally, given that we will be completing the nicotine exposure session among pregnant smokers who report current daily smoking, it is possible that we will have a biased sample. However, the ethical concerns of administering nicotine to a pregnant woman who has quit smoking, makes this limitation unavoidable. Therefore, to investigate the possibility of a biased sample difference in associations between sex hormones (Prog, Allo, E2/P) with smoking-related symptomatology and nicotine response we will also look at a subgroup of women who reduced their smoking during pregnancy (>50% reduction) versus those who maintained their self-reported pre-pregnancy smoking rate. Specifically, we will include an indicator variable for smoking reduction and the interaction between this indicator and sex

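### In the available text, no step after entry applies the plan's own condition that only pregnant women who report current daily smoking are given nicotine

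*Combined protocol and SAP*

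**What the plan says.** Strengths & Limitations states who should receive nicotine: "we will be completing the nicotine exposure session among pregnant smokers who report current daily smoking". The reason follows: "the ethical concerns of administering nicotine to a pregnant woman who has quit smoking, makes this limitation unavoidable". Entry to Sample 1 rests on self-report of at least 5 cigarettes a day over the past year (Sample 1 – Participants).

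After entry, Data Collection Procedures and Table 2 collect smoking information at several points:

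- Interim visit (Day 3 or 4): "Cigarettes smoked per day since Day 0 will be collected retrospectively from participants", with a CO reading.
- Table 2: "Expired Carbon Monoxide" at screening, Day 0, Day 6, Day 7 and Day 8, and urinary cotinine on Days 0, 6 and 8.
- Daily electronic assessments that include self-reported smoking.
- Day 6: "study staff may complete a NicAlert (Appendix C) to confirm self-reported smoking status". A cut-off is given (level 3 or above, cotinine at least 100 ng/mL), but no action for a lower result.

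The exposures are written as things that will happen. On Day 6 women "practice using the nicotine nasal spray but will be prompted to refrain from smoking for one hour prior to the visit to limit nicotine exposure", and they also practise smoking through the topography device. For Day 7 the text reads: "At this visit, participants will smoke their first morning cigarette". For Day 8, "instead of subject smoking a cigarette, they will administer nicotine nasal spray and repeat the protocol twice".

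**The concern.** The plan accepts a possibly biased sample so that nicotine is not given to a pregnant woman who has quit. That limit works only if someone checks it when the exposure is due. Entry status can be out of date by Day 6, and every woman is then told to stop by midnight, so some may decide to stay stopped.

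The plan foresees this for the oral contraceptive users. Sample 2 – Follow-up has staff ask whether each woman wants to go back to smoking, and expects up to 20% to prefer abstinence. No such question is described for pregnant women, whose cessation support comes after the testing period (Sample 1 – Follow-up). Followed as written, the text can lead staff to give a cigarette and nicotine spray to a woman whom the plan itself says should not receive nicotine.

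**Working it through.** **Step check, Sample 1.** Each step was read for a smoking-status condition.

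| Step | Smoking information | Action tied to it |
|---|---|---|
| Interim visit | CO, cigarettes per day | None stated |
| Day 6, before practice | CO and cotinine (Table 2); NicAlert optional | None stated |
| Day 6 spray practice | – | Unconditional |
| Day 6 practice smoking | – | Unconditional |
| Day 7 cigarette | CO before and after | Unconditional |
| Day 8 spray | CO, cotinine | Unconditional |

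Mandatory checks with a consequence: 0. Optional checks: 1, without a consequence. Exposures with no condition: 4.

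The Day 6 CO is worth using, because women are asked to go only one hour without smoking before that visit. On Days 7 and 8 CO says less, because overnight abstinence is instructed.

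**Exposure per affected woman.** Practice smoking and an unstated practice spray dose on Day 6, one cigarette on Day 7, and on Day 8 4 sprays × 0.5 mg = 2 mg of nicotine. The Day 8 amount is 4 mg if the repeated protocol means two doses.

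**Number affected.** The documents give no figure for Sample 1. At an assumed 1–5%: 112 × 0.01 = 1.1 and 112 × 0.05 = 5.6, so about 1–6 women.

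**The plan's own sample size.** 84 / (1 − 0.25) = 112, as stated. Power for r = 0.30, two-sided 0.05, by Fisher z is Φ(atanh(0.30) × √(n − 3) − 1.96), with atanh(0.30) = 0.3095. At n = 84 this is Φ(2.786 − 1.960) = 0.796. The noncentral t for the regression slope gives 0.813, which matches the stated 81%.

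**Cost of withheld sessions** (same Fisher z formula):

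- Losses absorbed by the drop-out allowance of 112 − 84 = 28: no change.
- 5% lost on top: 84 × 0.95 = 79.8, so n = 80 and power is Φ(2.716 − 1.960) = 0.775, about 78%.
- Upper-end analogue, 20% on top of 25%. Multiplied: 112 × 0.75 × 0.80 = 67.2, n = 67, power Φ(2.476 − 1.960) = 0.697. Added: 112 × 0.55 = 61.6, n = 62, power Φ(2.377 − 1.960) = 0.662.

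The 20% is the only related figure in the documents. It describes oral contraceptive users after a full testing period, so it is not an estimate for pregnant women during the week. Data collected before a session is withheld are kept, so these losses fall mainly on the abstinence and nicotine-response analyses (Hypotheses 2a and 2b).

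**The case against.** The best defence is that the limitations paragraph explains why the sample may be biased and was never meant as a check at each visit. The entry criterion applies the condition, the window is about a week, and staff see CO readings, cigarette counts and a NicAlert with a cut-off just before the Day 6 practice. Part of this stands: smoking is measured repeatedly, and it would be wrong to infer that no check exists. But no stated consequence follows any of these measures, and the only one aimed at confirming status is optional.

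Appendix C (cited at the NicAlert step), Appendix D (cited at the quit instruction) and the consent pages are not in the available text, and any of them could hold a rule. The point is limited accordingly.

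A check can also cost sessions and, if the wish to stay abstinent is related to craving, introduce selection into Hypothesis 2a. Both are fair and belong among the downsides.

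A reader might infer more than the documents support:

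- *That women are being harmed.* The text describes a low dose reviewed by a bioethicist, and nothing shows harm.
- *That the progesterone–craving estimate is biased.* No effect on it is shown. Craving readings after a stop would enter the Aim 1 average, but how many is unknown.
- *That pay leads women to conceal a stop.* Day 7, Day 8 and the completion bonus come to $20 + $50 + $100 = $170 of the stated $510 (33%). An incentive to stay silent is an inference, and the consent pages may cover part-payment.

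**Conclusion.** The gap is real on the available text: the plan sets an ethical limit on giving nicotine in pregnancy, and no visible procedure after entry applies it to any of the four exposures. Severity is minor to moderate. The conclusion rests on reading the procedures and does not depend on how many women stop. The 1–5% range is an assumption used only to scale the problem and its cost, and the 20% figure is an upper-end analogue. The point falls away if an appendix already holds a rule with a stated action.

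**What to change.** A cheap improvement, for Sample 1:

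- **Day 6, before either practice.** Staff will ask whether she has quit since enrolment. They will read the answer with the scheduled CO, the interim cigarette count and a NicAlert, changing *may* to *will*. The NicAlert is supporting evidence only: cotinine can miss a recent stop, and a low result alone should not exclude a woman who reports smoking.
- **Before the Day 7 and Day 8 exposures.** Staff will ask whether she has decided to quit, or wishes to stay abstinent beyond the overnight abstinence that the study requires. That instructed abstinence alone does not count as quitting.
- **If yes.** Withhold all remaining spray and cigarette procedures, offer cessation support at once, record the date and keep her data. Her pay should not be reduced for withheld sessions, unless the consent terms already cover this.
- **If Appendix C or D already holds such a rule,** cite it in the Day 6 paragraph.

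Optional: an Aim 1 sensitivity analysis using electronic assessments only up to the recorded stop date.

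The cost is a short question at three visits, up to about 112 NicAlert strips and some protocol wording. The pay clause adds nothing to the $510 already stated per woman. The downside is an unknown number of lost Day 6–8 sessions: no loss of power if they fall within the drop-out allowance, about 78% at n = 80 if they do not, and about 66–70% (62–67 completers) at the upper-end analogue. Report how many sessions were withheld, so that selection in Hypothesis 2a can be judged.
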